9.3 Demographics and Other Baseline Characteristics

Descriptive summaries of the demographic and other baseline characteristics will be completed for the ITT population. Baseline summaries will be presented overall, by treatment group (as randomized) and for the two subgroups “AAD only within Control Group” and “Cross-over within Control Group”.

Descriptive summaries of demographic and other baseline conditions will include:

- Demographics (Age, Gender) (ITT)
Imbalances between treatment groups will be tested by a Wilcoxon rank sum test for age and a Fisher test for gender.
- Cardiovascular Medical History (ITT Population) including
 - Lone AF
 - Reversible AF
 - Previously diagnosed with persistent/permanent AF/AT
 - Previously required cardioversion >48 hours after onset of AF/AT
 - Heart disease (including history of angina, congestive heart failure, hypertension, ischemic cardio-myopathy, non-ischemic

- dilated cardio-myopathy, hypertrophic obstructive cardio-myopathy, significant valve disease, valve replacement/surgery, congenital heart disease, left ventricular hypertrophy, myocardial infarction, Percutaneous Coronary Intervention (PCI), Coronary Artery Bypass Graft [CABG]), heart transplantation).
- Micro-/Thromboembolisms (by type of micro-/thromboembolism)
- Other arrhythmia (by type of other arrhythmia)
- Hemorrhagic Stroke
- Other Medical History (significant pulmonary disease, obstructive lung disease, diabetes, hyperlipidemia/dyslipidemia, renal insufficiency, and dementia)
- Prior Procedures
- AF History (time since first experience of AF, number of episodes in the past 6 months and HATCH score)
- Cardiovascular medication history (Previously failed therapeutic strategies by generic drug name, historical maximum dose by generic drug name converting all doses to the same unit (mg))

9.4 Study Treatment

The study treatments will be summarized according to the following features:

- Number of subjects in Control group with crossover to a RF ablation
- First ablation procedure (index ablation procedure in test group)
 - Anticoagulation strategy
 - Catheter used
 - Ablation catheter inserted (Y/N)
 - RF ablation performed (Y/N)
 - Heart rhythm at start
 - PV ablation (Y/N)
 - RF energy delivery time
 - Ablation outcome (complete PVI achieved: Y/N, entrance block confirmed: Y/N, sinus rhythm at the end of the procedure: Y/N, electrical cardioversion at the end of the procedure: Y/N, sinus rhythm post electrical cardioversion: Y/N)
- Baseline Medication regimen (same as pre-study, new) (drug therapy group only)
- Cardiovascular Medication (see below)

Summaries of Cardiovascular Medication: Cardiovascular Medication will be coded using the WHO Drug Dictionary (September 2011 or newer). Incidences of cardiovascular medications will be summarized by ATC level 2 and ATC level 4, if

applicable, and by treatment group, unless otherwise specified. The following summaries of incidences will be prepared including test and control group:

- Cardiovascular medication at baseline: All cardiovascular medication which was started before/at date of randomization and was not discontinued before/at date of randomization will be included in this summary.
- Cardiovascular medication started after baseline: All cardiovascular medication which was started after date of randomization will be included in this summary. This may include dose changes after baseline if these are recorded as new medication entries.
- Concomitant cardiovascular medication: All cardiovascular medication which was started at any time during study and was not discontinued before/at date of randomization will be included in this summary.

In case start and/or end date are incomplete, a medication will be analyzed as concomitant medication as long as it cannot definitely be shown that the medication was discontinued before date of randomization. For concomitant medications, in case it cannot unequivocally be decided if the medication started before or after baseline, these will be analyzed as baseline medication, but excluded from medication started after baseline.

Additionally to these general medication summaries, summaries of new AADs started after baseline will be prepared as described in section 10.6.2).

10. EFFICACY ANALYSIS

Formal planned analyses are described below. It may be necessary for additional exploratory analyses to be completed in this study after results from the planned analysis are completed. Full details of additional analyses will be given in the CSR.

10.1 Primary Efficacy Variable Analysis

The primary analysis will be a Kaplan-Meier (KM) analysis for all subjects in the ITT population and account for censored observations. The primary effectiveness analysis will be performed in the ITT population, where the subjects will be attributed to the treatment group as randomized, regardless of treatment cross-over or post-randomization medical care. A log-rank test will be used to compare the hazard functions between the two groups at any observed event time. If observed, the median time to persistent AF/AT as well as the 95% confidence intervals will be reported by treatment group based on Kaplan-Meier estimates. The rate of survival without persistent AF/AT and rate of persistent AF/AT at 3 years follow-up as well as the 95% confidence intervals for both groups will be presented using the product limit estimate from the Kaplan Meier curve. Kaplan-Meier curves will be plotted.

The effect size is defined as the negative log of the hazard ratio (hazard rate of the Test Group over hazard rate of the Control Group): $\delta = -\log_e(\lambda_t/\lambda_c)$.

This study is to test the following hypothesis using a one-sided test at alpha equal to 0.025:

H0: $\delta \leq 0$

H1: $\delta > 0$

Null hypothesis: the hazard rate in the Test Group is greater than or equal to the hazard rate in the Control Group at observed event times during the follow-up period

Alternative hypothesis: the hazard rate in the Test Group is less than the hazard rate in the Control Group at observed event times during the follow-up period

Subjects will be considered to have an effectiveness success if they do not progress to persistent AF/AT through the 3-year follow-up period.

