3.3 Method of Treatment Assignment and Randomization

Subject randomization will be 1:1 between catheter ablation (Test) and AAD therapy (Control). The randomized block design, stratified by gender and site, will be used to ensure a gender balance by treatment group at each site. Adaptive randomization will also be executed to further ensure the allocation balance of treatment groups by gender at each site. Subjects will be randomized in the order of their enrollment.

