6. SAMPLE SIZE DETERMINATION

A total sample size of 322 (161:161) subjects will be required to ensure 85% power to detect the effect size measured by negative log of the hazard ratio equal to 1.1541 (treatment group over control group).

$$-\log_e \left(\frac{\hat{\lambda}_t}{\hat{\lambda}_c} \right) = -\log_e \left(\left(-\frac{\log_e(0.95)}{3} \right) / \left(-\frac{\log_e(0.85)}{3} \right) \right) = 1.1541$$

This calculation assumes a 50% cross-over rate from the AAD group to the ablation group, a 10% drop-out rate in each group over the 3 year follow-up period, and 1.5 years accrual time. This calculation is based upon one-sided superiority testing with alpha equal to 0.025. Using meta-analysis, the rates of disease progression at the end of follow-up are estimated to be 25% and 5% in the AAD and ablation group, respectively (see the point estimate justification document for details, Appendix C of the CTP). The cross-over to ablation is reflected in the use of the proportion 0.85 instead of 0.75 in the formula above. The sample size calculation is based upon the method developed by Rubinstein, Gail and Santner⁴ (RGS, 1981) and also incorporates group sequential design with multiple interim looks.

Adaptive Sample Size Re-estimation

Due to the uncertainties associated with the cross-over rate and the effect size, the sample size will be reestimated at the time of the first interim analysis. Conditional power (CP) will be calculated at that time to determine how promising the interim results are. CP is defined as the conditional probability that the final result will exceed a critical value given the data observed thus far, and the assumption that the trend to be observed in the remainder of the study⁵ will follow the expectation, which was used in the original sample size calculation. If the CP is less than 0.3, then the study is considered not promising, and the sample size will not be increased. If the CP is

greater than 0.9, then the study is deemed fully powered and the sample size will not be increased. If the CP falls in the promising zone (0.3-0.9), the sample size will be re-estimated based upon the observed effect size.

In detail, the following formula will be applied to re-estimate the sample size:

$$M = N \left(\frac{\delta}{\Delta} \right)^2$$

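### Randomization is stratified by gender and site, but the primary log-rank uses neither factor and no design-aligned ITT hazard ratio is planned: a small, inexpensive gain left unused, not an error

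*SAP*

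**What the plan says.** **Allocation.** SAP 3.3 states: "The randomized block design, stratified by gender and site, will be used to ensure a gender balance by treatment group at each site". Adaptive randomization is added on top. Protocol 13.5 says the same.

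**Primary test.** SAP 10.1 states: "A log-rank test will be used to compare the hazard functions between the two groups at any observed event time". Protocol 13.9.1 uses the same sentence. Neither names a stratum or says why none is used. The standardized log-rank score used at the interim looks (SAP 10.4) names none either.

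**Effect estimate.** SAP 10.1 defines the effect as the negative log hazard ratio. For the ITT population it then plans medians, 3-year rates with confidence intervals, curves and the log-rank test, and planned table 14.2.1.1 lists only the Kaplan-Meier and log-rank results. A treatment hazard ratio with its interval is specified only in SAP 10.2, for the as-treated Cox model in the per-protocol population.

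**Where the factors do appear.** Gender is one of the candidate covariates in the factor-screening Cox models of SAP 10.6.4. Protocol 13.15 had a conditional site-adjusted Cox analysis of the ITT comparison, but SAP 5.1 drops the site-heterogeneity analysis.

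**Timing.** SAP 8.3 records that interim analyses were run under SAP version 1.0. SAP 5.1 records that the study ended early and that the final test spends the remaining alpha.

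**The concern.** Stratified allocation forces the arms to be balanced within gender. If gender affects progression, an unstratified log-rank takes no credit for that balance, so it is slightly conservative and its implied hazard ratio is pulled slightly towards 1. A test stratified by gender recovers this and needs no extra data, because gender is known for everyone. The planned final analysis has only 28 events, so even small gains deserve a look.

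The second issue is the estimate. The trial's own effect measure is a hazard ratio, and as planned the ITT comparison would be reported without one that reflects how subjects were allocated.

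**Working it through.** **1. The plan's own figures.** SAP 6 gives "A total sample size of 322 (161:161) subjects will be required to ensure 85% power", "negative log of the hazard ratio equal to 1.1541" and "This calculation is based upon one-sided superiority testing with alpha equal to 0.025". The 3-year rates are 5% on ablation and 15% on drug therapy after cross-over, since "The cross-over to ablation is reflected in the use of the proportion 0.85 instead of 0.75 in the formula above".

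- Hazards per year: −ln(0.95)/3 = 0.01710 and −ln(0.85)/3 = 0.05417. The hazard ratio is 0.3156 and δ = 1.1532 (the SAP prints 1.1541, an immaterial difference).
- Events (Schoenfeld, 1:1): 4(1.960 + 1.036)²/1.1532² = 27.004, rounded up to 28. This matches the final look in the SAP 10.4 table.
- Subjects (Rubinstein-Gail-Santner): n per arm = (z_crit + 1.036)²/δ² × (1/p_t + 1/p_c). With 10% drop-out, 1.5 years of accrual and a common closing date, p_t = 0.0582 and p_c = 0.1723. The total is 310.5 at z_crit = 1.96 and 329.6 at the final boundary 2.0507, so 322 lies between. With exactly 3 years of follow-up per subject the same formula gives 379 to 402. A two-proportion formula for 5% against 15% gives exactly 322.

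None of these calculations uses gender or site.

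**2. Power with and without stratification.** Simulated trials had N = 322, blocks of 4 within gender-by-site strata, the hazards above, 10% drop-out, a 3-year cap and one final test at 2.0507. There were 8,000 runs per row and about 30 events per trial. Assumptions not in the documents: 40% women, the gender hazard ratios shown, 50 sites with equal expected enrolment, no site effect and the block size. Average hazard was held fixed as the gender effect varied.

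| Gender hazard ratio | Unstratified | By gender | By gender and site |
|---|---|---|---|
| 1 | 83.3% | 83.2% | 76.2% |
| 1.5 | 83.4% | 83.3% | 75.4% |
| 2 | 81.4% | 81.7% | 73.4% |
| 3 | 81.4% | 82.3% | 72.9% |

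The change from gender stratification is −0.1, −0.1, +0.3 and +0.9 points (paired simulation standard errors 0.1 to 0.2). Repeat runs at the same boundary gave −0.1, +0.3 and +0.8 points (5,000 trials per setting) and 0.0, +0.4 and +1.0 points (10,000 trials per setting) at gender hazard ratios 1, 2 and 3.

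**3. Why site cannot be included.** Up to 50 sites and two genders make up to 100 strata: 322/100 = 3.2 subjects and 28/100 = 0.28 events per stratum on average. In the simulation about 3 to 4 of some 30 events fell where only one arm was at risk and so carried no information. The loss was 7.1 to 8.5 points. With 30 sites and no gender effect (4,000 runs) power went from 82.0% to 79.6%, a loss of about 2 points.

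**4. Level.** One-sided type I error at 1.96 for gender hazard ratios 1, 2 and 3 (8,000 runs, simulation standard error about 0.0017):

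- unstratified: 0.0256, 0.0249, 0.0238
- by gender: 0.0261, 0.0258, 0.0265

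All lie within about one standard error of 0.025. In the 10,000-trial runs the two Z statistics correlated at 0.998 to 0.9998.

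**The case against.** Four arguments can be made for leaving the plan alone.

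- **The test is sound and little is lost.** This stands. The level is held, and any visible gain needs a gender hazard ratio of 2 to 3. The documents do not show that gender is prognostic: the review of predictors in Protocol 5.1 covers age, left atrial size, hypertension, valvular disease, heart failure and the HATCH score, and HATCH has no gender item. Gender is only a candidate factor.
- **A gender-only test is not the allocation scheme.** This also stands. Allocation is by gender within site, so gender stratification reflects it only in part. The full match costs power, which makes gender alone a pragmatic choice.
- **Changing the primary test now has a price.** This stands and limits the fix. Comparative looks have been taken in an open-label trial with sponsor-adjudicated events, using a statistic with no strata. The high correlation means the boundaries would hardly be disturbed, and SAP 5.1 already changes the time origin for the final analysis. Even so, a gain of at most about 1 point does not justify replacing the alpha-controlled test at this stage.
- **SAP 10.6.4 already covers gender.** This stands only in part. Its single-covariate model includes a gender-by-treatment interaction, so its treatment coefficient is not an overall effect. Its multivariable model selects terms stepwise. Neither is a clean estimate of the primary comparison.

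**Conclusion.** The mismatch is real and small. Both randomization factors are absent from the primary log-rank, and no ITT hazard ratio that respects the design is planned. Stratifying by gender is worth about 0 points of power if gender is not prognostic and up to about 1 point at an assumed gender hazard ratio of 3. It needs no extra alpha, subjects or events. These figures rest on 40% women, constant hazards and about 30 events. The documents do not give the event count after early termination.

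A reader might infer that the planned test is invalid, that the trial gives up meaningful power, or that the analysis must carry every randomization factor. The documents and the calculations do not support any of these: the unstratified test holds its level, the difference is at most about 1 point, and including site would do harm. The point concerns efficiency and reporting. The more useful part of the remedy is the ITT hazard ratio.

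**What to change.** In Protocol 13.9.1, the clean specification is a log-rank stratified by gender at all looks.

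Because interims have already used the unstratified statistic, SAP 10.1 and 10.5 should, before database lock:

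1. State that the alpha-controlled primary test remains the unstratified log-rank, for consistency with the interim boundaries.
2. Pre-specify, in the ITT population, a gender-stratified log-rank as a named sensitivity analysis, and a gender-stratified Cox hazard ratio with 95% CI as the reported effect estimate.
3. State that site is not used as a stratum, because gender-by-site strata are too sparse for the expected number of events.

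The cost is a STRATA statement in each of two procedures, a few sentences in the SAP and an added block in the planned primary efficacy table. No new data are needed.

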10.2 PP analysis

The Kaplan-Meier analysis as described in section 10.1 will be repeated in the PP population (based on the as-treated principle).

Moreover, an inferential analysis using a Cox proportional hazards model will be performed in the PP subject population. For the Cox proportional hazards model, treatment itself will be modelled as a time-dependent covariate, i.e:

- for control group (without cross-over): treatment at time t is “control” at any time t
- for ablation group (without cross-over): treatment at time t is “ablation” at any time t
- for cross-over group: treatment at time t is control at any time t before cross-over and ablation at any time t after cross-over

The Cox proportional hazards model will be used to compare the hazard rate between the two treatment groups at observed event times.

The hazard ratio and its 95% confidence interval will be reported. Missing primary effectiveness endpoint data will be censored at the time of the subject’s last visit/TTM.

The same principles outlined for section 10.1 also apply for section 10.2 (PP analysis).

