### 13.11 Secondary Statistical Analyses of Primary Effectiveness Endpoint

#### 13.11.1 Per-Protocol Analysis

This analysis will be performed in the PP subject population. Propensity score weighting methodology will be applied to adjust for the imbalance of subjects' characteristics between these two groups. Cross-over subjects will be added to the ablation group and the time-dependent covariate will be used to account for the different timing of cross-over. A propensity score weighted Cox proportional hazards model will be used to compare the hazard rate between the two groups at observed death times. Diagnosis analyses will be performed to examine the assumption of proportional hazards. If the proportional hazards assumption is not met, then the interaction effect of time by treatment group and other remedy analyses will be investigated. The adjusted hazard ratio and its 95% confidence intervals will be reported for the two groups. Missing primary effectiveness endpoint data and the associated covariates that will be included in the propensity score modeling will be imputed using the multiple imputation method.

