## Appendix B: Guidelines and Restrictions for the ATTEST Protocol Regarding Cross-over from the Drug (Control) Group

1. Guidelines and principles for cross-over are to be followed by the investigator as laid down in this document and in the protocol.
2. It is the intent of the Sponsor and organizers of this study that cross-over be significantly reduced from published rates quoted in previous drug versus ablation trials.
3. The crossing over from the drug group undermines the tenets of equipoise that are intended in: (a) the study's collective inclusion/exclusion criteria for all subjects; (b) the eligibility of all subjects at study onset to be randomized to either treatment group; and, (c) the intended balance of AF severity, drug history, concurrent illnesses (HATCH score severity), demographics, and other characteristics, such that legitimate statements might be made in comparing the outcomes of medical management versus ablation therapy. The nature and conditions for cross-over from the Control (AAD therapy) Group to the Test (PVI) Group, in a randomized controlled study, are not well understood and are multi-factorial. Thus, any assumptions that subjects crossing over reflect the general demographics, disease severity, and extent of disease progression within either study group at randomization cannot be held with certainty.
4. One could justifiably argue that those most likely to suffer severe side effect reactions from AAD therapy might be those who take their drugs sporadically, take drugs sometimes too close together (shortened inter-dose time interval), suffer rebound effects from resumption of drugs after a drug holiday, and who do not heed the warnings of physicians/pharmacists about mixing drugs for AF/AT with those for other chronic diseases. One might further argue that those with heightened disease progression, as noted in published literature, would be among the oldest in their randomized study group and that their baseline HATCH scores are likely to be high as well, which is consistent with elderly patients. If one or more of these assumptions are true, those most likely to seek cross-over from the drug group would be among the aforementioned, resulting in a relatively younger, healthier, and more compliant group of subjects remaining in the drug group over the whole 3 year study period. In this context, extensive cross-over certainly would erode equipoise.

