5. CHANGES TO PLANNED ANALYSIS

5.1 Changes for the final analysis

As the study was terminated early, without having met primary effectiveness or futility criteria at the most recent interim analysis, it is not fully obvious which alpha level to use for the primary efficacy analysis. However as the number and time points of the interim analyses had not been fixed in advance, it was decided to spend all alpha remaining for the final analysis, in other words to spend what is left from the total alpha. Moreover, after further discussion, it has been decided to update the calculation of the primary endpoint to use procedure date as start date for time to event calculation rather than randomization date (see section 8.3).

It also was decided to delete some of the analyses originally planned in the protocol:

- For secondary endpoint “factors associated with AF disease progression”, only the main analyses will be performed, and some of the supporting models were deleted
- Analysis of site heterogeneity will not be performed

Moreover, a sensitivity analysis for the primary endpoint and first secondary endpoint was added, using an alternative definition for the primary endpoint based on the consensus statement of the HRS (Heart Rhythm Society, 2017).

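### SAP 10.2 drops the protocol's propensity weighting from the as-treated per-protocol Cox model without declaring it, so that hazard ratio is open to baseline confounding

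*SAP*

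**What the plan says.** **Protocol 13.11.1 (Per-Protocol Analysis).** "Propensity score weighting methodology will be applied to adjust for the imbalance of" subject characteristics between the two groups. Cross-over subjects join the ablation group, with a time-dependent covariate for the timing. The model is weighted: "A propensity score weighted Cox proportional hazards model will be used to compare the hazard rate between the two groups at observed death times". The result is an adjusted one: "The adjusted hazard ratio and its 95% confidence intervals will be reported for the two groups".

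**SAP 10.2 (PP analysis).** The time-dependent part survives: "treatment itself will be modelled as a time-dependent covariate". The comparison is then described as "The Cox proportional hazards model will be used to compare the hazard rate between the two treatment groups at observed event times". No weights and no baseline covariates are named, and the output is a plain hazard ratio with its 95% interval. Propensity scores are mentioned nowhere in the SAP.

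**SAP 5.1 (Changes for the final analysis).** "It also was decided to delete some of the analyses originally planned in the protocol". Two items follow: some supporting models for the progression-factors endpoint, and the site-heterogeneity analysis. Neither covers the PP Cox model.

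**SAP 7 and SAP 6.** PP analyses are as treated, and the sample size assumes that 50% of the control group crosses over.

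**Protocol Appendix B, item 3.** The protocol warns that "any assumptions that subjects crossing over reflect the general demographics, disease severity, and extent of disease progression" within either randomized group cannot be held with certainty.

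**The concern.** Once control patients who have an ablation contribute follow-up to the ablation side, the comparison no longer rests on randomization alone. Coding treatment as time-dependent deals with when a patient crosses over. It does not deal with which patients cross over. If baseline risk predicts cross-over, the treatment coefficient in SAP 10.2 mixes the effect of ablation with the difference in risk between those who switch and those who stay.

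The protocol's answer was prespecified weighting. With that gone and the change not listed, a reader of the final report could take the PP hazard ratio for the adjusted one that the protocol promised. At stake is the reading of a secondary analysis that will be set beside the ITT result.

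**Working it through.** **1. The two plans side by side**

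| Element | Protocol 13.11.1 | SAP 10.2 |
|---|---|---|
| Cross-over timing | time-dependent covariate | time-dependent treatment |
| Baseline adjustment | propensity weights | none |
| Estimate | adjusted hazard ratio | hazard ratio |
| Proportional-hazards checks and remedies | planned | not mentioned |

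**2. Is the change declared elsewhere?** The SAP declares other departures where they occur: 8.1 explains the change of population for health economics and quality of life, and 8.2 drops multiple imputation for the time-to-event outcome. Neither mentions the weighting.

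**3. Could baseline risk matter?** Protocol 5.1 cites annual progression of 25-40% for HATCH 2-7 against below 10% for HATCH 0-1. The eligible range (HATCH 1-4) straddles that cut. Appendix B, item 4, describes a conditional scenario in which older, higher-HATCH patients leave the drug group.

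**4. How far does SAP 10.6.4 make up for it?** In the PP population it fits time-dependent treatment with baseline covariates.
- Candidates are screened at p<0.2, then chosen stepwise at 0.05. There are 13 candidates and 28 planned events (SAP 10.4): 28/13 = 2.2 events per candidate. A real confounder may be dropped because it misses a p-value threshold.
- LA size is split at 55 mm, which is the eligibility limit. SAP 9.2 generally excludes major eligibility deviations from the PP population, so this covariate is nearly constant. Baseline dementia, which the protocol says precludes enrolment, is nearly constant too.
- The model serves the progression-factors endpoint and is not named as the adjusted PP comparison.

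**5. Illustrative size.** The documents give no figure for differential cross-over, so these inputs are assumptions: no true effect of ablation, a binary risk factor with 40% prevalence and hazard ratio 2-3, and cross-over of 65-75% in high-risk against 33-40% in low-risk patients. Simulated rate ratios, ablation time against drug time:

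| Unadjusted | Adjusted for the factor | Ratio |
|---|---|---|
| 1.02 | 0.98 | 1.02/0.98 = 1.04 |
| 1.07 | 1.00 | 1.07/1.00 = 1.07 |
| 1.12 | 1.01 | 1.12/1.01 = 1.11 |

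That is a bias of about 4-12% (12% if 1.12 is set against the true value of 1). Other assumptions move it:
- the same inputs in a two-arm simulation with 25% control risk at 3 years: 1.06-1.16, and 1.00 after stratifying on the factor;
- 50% prevalence, hazard ratio 3, cross-over 80% against 20%: up to 1.26;
- cross-over unrelated to risk: 1.01;
- low-risk patients crossing over instead: 0.90.

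**6. Against sampling error.** With 28 events the standard error of the log hazard ratio is at least √(4/28) = 0.378, so the 95% interval spans a factor of about exp(1.96 × 0.378) = 2.1 each way. The shift is ln(1.04)/0.378 = 0.10 to ln(1.12)/0.378 = 0.30 standard errors. Even 1.26 gives ln(1.26)/0.378 = 0.61.

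**7. On the planning effect.** The design hazard ratio is ln(0.95)/ln(0.85) = 0.316. A 4-12% shift would move it to 0.316 × 1.04 = 0.33 or 0.316 × 1.12 = 0.35.

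**The case against.** The strongest reply is that little hangs on this. The analysis is secondary (SAP 8.2 calls it a sensitivity analysis), the expected bias is a fraction of a standard error, and an unweighted model is a defensible choice when events are sparse. The SAP also lets selection be seen: 9.3 tabulates baseline characteristics separately for control patients who stayed on drugs and those who crossed over, and 10.3 shows cross-overs as a third Kaplan-Meier group. All of this stands, and it limits the weight of the point. It does not explain why the change is undeclared.

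A second reply is that baseline adjustment cannot remove what drives cross-over. Appendix B, item 7, lists reasons that arise after randomization: severe symptoms, side effects, adherence and lack of further drug options. This also stands. Weights or covariates measured at baseline help only so far as they predict those reasons.

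A reader might infer that no safeguard is left, or that the PP result will flatter ablation. The documents support neither. SAP 10.6.4 retains a covariate-adjusted PP model, though a data-selected one. Under the Appendix B scenario the bias runs against ablation; it would favour ablation only if lower-risk patients were the ones to cross over.

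**Conclusion.** The point holds as an undeclared removal of a prespecified adjustment. It leaves the SAP 10.2 hazard ratio open to baseline confounding, in a direction that depends on who crosses over. If higher-risk patients do, the bias is against ablation and about 4-12% under the stated assumptions, which is small beside the sampling error with about 28 events. The prevalence, risk-factor strength and cross-over split are assumed. The 28 events are the planned number; SAP 5.1 says that the study was terminated early, and the SAP does not give the final count.

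It would be wrong to read this as a threat to the main conclusion. The ITT log-rank test, its hypothesis and its stopping boundaries do not depend on the PP model.

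**What to change.** In SAP 10.2:
- Keep the current model and label its hazard ratio unadjusted.
- Beside it, report the hazard ratio from the same time-dependent Cox model with three baseline covariates that are already collected, fixed in advance and entered without selection: for example continuous age, continuous LA diameter and HATCH score. Alternatively, reinstate the protocol's propensity weights.
- State that baseline adjustment does not remove confounding by reasons for cross-over that arise after randomization.

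In SAP 5.1, list the departure from protocol 13.11.1 and give the reason.

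The set should stay at three. Age, LA diameter and the five HATCH components entered separately would be up to seven terms, or 28/7 = 4 events each; three covariates leave 28/3 = 9.3. HATCH already contains a point for age over 75, so it overlaps a little with continuous age, which is acceptable in an adjustment model.

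The cost is one extra model statement, a line in the change list and a slightly wider interval for the adjusted estimate with few events. No new data are needed.
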